Cluster Randomization. The four OnPoint syringe exchange locations will be randomized to deliver either the active (intervention) or didactic (control) version of the LinkUP intervention. The randomization scheme will be developed using an algorithm by La Frontera's statistician. Approximately three months into enrollment, there will be a one-week 'washout' period, after which time the two original intervention syringe exchange sites will become control sites and the two original control sites will become intervention sites. This cluster randomization scheme will help ensure that no neighborhood in San Diego County is denied access to the LinkUP intervention. By the end of the study, 75 LinkUP participants will have been randomized to an intervention site and 75 will have been randomized to a control site.

Participant Intake and Out-take Data at OnPoint Locations. OnPoint peer counselors will confirm that their client is a LinkUP participant when they are presented with the laminated card that was provided by LinkUP staff. They will then conduct a short 5 minute interview with the participant to obtain information on their COVID testing and vaccination history, their health status and any of their harm reduction needs to facilitate any referrals. After their visit, the peer counselor will supplement this with the Out-take data, which includes whether or not the participant received the LinkUP intervention and COVID-19 test(s). The information obtained will be shared through record linkage between OnPoint and La Frontera to confirm the study outcomes. Following the intake interview, the participant will either receive the LinkUP active or didactic intervention depending on the randomized allocation of the SSP site.

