Outcome Ascertainment: COVID-19 Testing & Vaccination. Outcome ascertainment will involve record linkage between La Frontera and OnPoint to determine which participants visited the SSP site they were referred to, and if they received the LinkUP intervention and COVID19 tests. Since LinkUP participants who refused COVID-19 tests at the SSPs and will have obtained COVID19 vaccination elsewhere, we will obtain these data in three ways: 1) *Self-report from La Frontera follow-up interviews* conducted 6 months after randomization. 2) *Record linkage with the CDPH's COVID-19 database* based on electronic health records (EHRs) for participants who provided a release of medical information. Record linkage will confirm if and where COVID testing was done elsewhere, if COVID-19 vaccine was administered, type, dates and # of doses, as well as hospitalizations and deaths. 3) *Biological validation* of vaccination will also be done based on COVID-19 serology conducted by Genalyte, which is being conducted as part of their follow-up visits in the parent study, La Frontera.

Analysis: Although the LinkUP trial is not powered to assess efficacy, we will conduct an intent-to-treat analysis following CONSORT guidelines[24] and register it at clinicaltrials.gov before enrolment. We will compare socio-demographics across the two study arms (intervention and control) to ensure balance, controlling for potential confounders and study location if there are significant differences. To obtain effect sizes and standard errors, percentages along with 95% CIs for those who a) had a COVID test within 6 months of the intervention and b) had \geq one COVID shot within 6 months of intervention, respectively, will be calculated for the two study arms. To obtain Risk Ratio estimates (intervention/control), we will use a logistic regression mixed model with a) had a COVID test; and b) had \geq 1 COVID shot within 6 months of intervention, respectively, as outcomes, considering intervention (active vs. didactic) as the primary fixed effect, potential covariates (e.g., age, gender, homelessness, income) and a random intercept for subject. We will also assess acceptability and feasibility of the LinkUP intervention among OnPoint investigators, staff, and clients through focus groups and CSAB meetings.

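### Risk ratios are to come from a logistic mixed model with a subject random intercept: no step from its conditional odds ratio to a risk ratio is given, and one binary value per subject cannot support the intercept

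*Combined protocol and SAP*

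**What the plan says.** The plan is in section 9 of the combined protocol and SAP, Analysis paragraph. The effect measure and the model are named together: "To obtain Risk Ratio estimates (intervention/control), we will use a logistic regression mixed model". Arm is the main fixed effect, demographic and social covariates may be added, and the only random term is "a random intercept for subject".

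The two outcomes (any COVID test; at least one vaccine dose) are fitted separately, each as a single cumulative yes/no: "COVID shot within 6 months of intervention, respectively, as outcomes". Under Outcome Ascertainment, the one self-report time point named is the parent-study interview "conducted 6 months after randomization".

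The same paragraph plans a simpler summary for each arm: "To obtain effect sizes and standard errors, percentages along with 95% CIs". It also limits the trial's ambition: "Although the LinkUP trial is not powered to assess efficacy". Section 5 nevertheless says that the results will supply effect sizes for a later efficacy trial.

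No part of the document gives a log link, marginal standardisation, a ratio of predicted probabilities, or a delta-method or bootstrap step that would turn the logistic coefficient into a risk ratio.

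**The concern.** There are two linked problems.

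- **Target and tool do not match.** Exponentiating the arm coefficient of a logistic mixed model gives an odds ratio conditional on the subject's intercept. Whenever there is an effect, that number lies further from 1 than the risk ratio: slightly for a rare outcome, a lot for a common one. With no effect both equal 1. The plan does not say that the exponentiated coefficient will be reported as the risk ratio, but it does not say what will be done instead, and the answer depends on it.
- **The subject intercept has nothing to estimate.** A subject random intercept describes correlation among repeated values from one person. Here each person gives one value per model. With arm alone in the model the variance is not identified, so the conditional odds ratio has no determinate value. With covariates it is pinned down only by the assumed distribution of the intercept. A conversion that predicts risks at intercept zero inherits this arbitrariness.

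At stake is the effect estimate carried into the later trial. If a mislabelled odds ratio were used for planning, that trial would be too small.

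**Working it through.** **Inputs.** 75 participants per arm, 75 + 75 = 150 (section 9, Cluster Randomization). One binary value per participant per outcome (section 9, Analysis). The plan states no power, effect size, risk ratio (RR) or odds ratio (OR), so there is no figure to reproduce. All arm rates below are assumptions. Section 7 reports 9% vaccinated, 32% previously tested and 55% willing to be vaccinated in the parent cohort. LinkUP enrols only people never tested outside that study and never vaccinated, so these are not arm rates; they show only that a rare outcome cannot be taken for granted.

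**Step 1: ordinary OR for a given RR.** With control risk pc and active-arm risk pa = RR × pc, OR = [pa/(1 − pa)] / [pc/(1 − pc)]. Example: pc = 0.40, RR = 1.5, pa = 0.60, OR = (0.60/0.40)/(0.40/0.60) = 2.25.

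| True RR | pc 9% | pc 20% | pc 40% | pc 50% |
|---|---|---|---|---|
| 0.8 | 0.78 | 0.76 | 0.71 | 0.67 |
| 1.0 | 1.00 | 1.00 | 1.00 | 1.00 |
| 1.2 | 1.22 | 1.26 | 1.38 | 1.50 |
| 1.5 | 1.58 | 1.71 | 2.25 | 3.00 |

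**Step 2: identifiability, arm-only model.** Assume 30/75 control and 45/75 active events. For subject SD s and standard normal u, the model's arm risks are E[expit(a + su)] and E[expit(b + su)]. For any s, a and b can be chosen to give exactly 0.4 and 0.6. The maximised log-likelihood is then always 60 ln 0.4 + 90 ln 0.6 = −54.9774 − 45.9743 = −100.952. The conditional OR is exp(b − a). The RR averaged over u is 0.6/0.4. The RR at u = 0 is expit(b)/expit(a).

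| Subject SD | Log-likelihood | Conditional OR | RR averaged over intercept | RR at intercept zero |
|---|---|---|---|---|
| 0 | −100.952 | 2.25 | 1.50 | 1.50 |
| 1 | −100.952 | 2.66 | 1.50 | 1.63 |
| 2 | −100.952 | 3.80 | 1.50 | 1.95 |
| 4 | −100.952 | 9.18 | 1.50 | 3.03 |

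The data cannot choose between these rows. Only the averaged RR is stable.

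**Step 3: with covariates.** The simulation used 150 participants, arm log-OR 0.85, two continuous and two binary covariates, true subject SD 0, and 100 data sets per setting, with the likelihood maximised at SD 0, 1, 2 and 4.

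- The log-likelihood differed across SDs by a median of 0.03 (covariate coefficients ±0.3) or 0.10 (±0.6), and by 0.69 at most. Excluding an SD at the 95% level needs 1.92.
- The median conditional OR ran from 2.4–2.5 at SD 0 to 10.5–10.8 at SD 4.
- The RR averaged over the intercept stayed at 1.50 and 1.46 in the two settings. The RR at intercept zero ran from 1.51 to 2.38 and from 1.46 to 1.84.

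A separate simulation with three weaker covariates and SD 0 to 3 gave a median log-likelihood range of 0.018 (95th percentile 0.069).

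**Step 4: consequence if mislabelled.** Assume control risk 32% and true RR 1.5, so pa = 0.48 and OR = (0.48/0.52)/(0.32/0.68) = 1.96. For an individually randomised trial with 80% power and two-sided 5%, n per arm = 7.85 × [pc(1 − pc) + pa(1 − pa)]/(pa − pc)².

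- RR 1.5: 7.85 × (0.2176 + 0.2496)/0.16² = 143.3, so 144 per arm.
- 1.96 taken as the RR, pa = 0.6272: 7.85 × (0.2176 + 0.2338)/0.3072² = 37.5, so 38 per arm.

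**The case against.** The strongest replies, and what remains of each:

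- **This is an omission, not an error.** A logistic model can give a correct RR by standardisation, and nothing says that the coefficient will be mislabelled. That stands for the conversion step, and it makes the harm conditional. It does not rescue the subject intercept, which is wrong for the data described.
- **Covariates identify the variance.** Formally yes, through the assumed distribution. In practice step 3 finds almost no information at 150 participants.
- **The large odds ratios come from imposed SDs.** True. They demonstrate non-identification and do not forecast the fitted result. Software that sets the variance to 0 returns the ordinary OR, which reduces the problem to step 1. That number is still not an RR.
- **A longitudinal model may have been meant.** The parent study is prospective, so this is possible. But each outcome is defined cumulatively over 6 months and no repeated outcome is described. Eligibility also makes a baseline value constant.
- **There is a crossover.** Sites switch: "after which time the two original intervention syringe exchange sites will become control sites". No participant is described as receiving both versions.
- **It is a pilot, and the arm percentages give a crude RR.** Both points stand and limit the consequences. The plan still assigns the RR to the model, and the results are meant to inform a later trial.

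**Conclusion.** The concern holds. The model as written does not yield the stated effect measure, and its only random effect cannot be supported by one binary value per subject.

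The size depends on assumed rates. If the ordinary OR were reported as the RR, a true RR of 1.5 would appear as 1.58 at 9% control risk, 1.71 at 20%, 2.25 at 40% and 3.00 at 50%. A nonzero imposed intercept variance pushes the conditional OR further out by an amount the data cannot determine. Risks averaged over the intercept, an ordinary standardised logistic model, or the crude arm percentages all avoid the problem.

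Because the trial is a pilot and a valid crude RR is available from the planned output, this does not undermine the study. It should be corrected before analysis, since the damage would come from using a mislabelled model estimate for planning.

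**What to change.** Remove the subject random intercept. State that the RR and its confidence interval come either from a modified Poisson (log-link) model, or from an ordinary logistic model by marginal standardisation over the trial sample. Label any odds ratio as an odds ratio. If the intercept was meant for site, or for a repeated outcome not described, say so and define that structure.

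This costs one or two sentences and standard software, with no new data.

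The intervals must also allow for the four-site crossover allocation. How they do so is a separate decision for the trial statistician; the present text only adjusts for location if the arms differ significantly. One option is to regress log risk in the eight site-by-period cells on arm, site and period, with a t interval on 8 − (1 + 1 + 3 + 1) = 2 degrees of freedom. It has a real price, shown by simulation: 150 participants, RR 1.5, control risk 20% or 40%, site SD 0.2, assumed site-by-period log-risk SD 0, 0.15 or 0.3, and 3,000 runs per setting.

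- **Coverage:** 95–96% in all six settings for the cell analysis, against 79–96% for an individual-level Poisson model with robust errors. The low value was at 40% risk and SD 0.3 (repeat runs gave 77–78%). It is approximate, because the log-risk model there generates some cell risks above 1.
- **Width with no site-by-period variation:** the median ratio of upper limit to estimate was 1.95 v 1.41 at 40% risk and 3.49 v 1.84 at 20% (repeat runs gave about 1.9 v 1.4 and 3.3 v 1.8).

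The correction to the RR does not depend on which interval is chosen.

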The four OnPoint syringe exchange locations will be randomized to deliver either the active (intervention) or didactic (control) version of the LinkUP intervention. Approximately three months into enrollment, there will be a one-week 'washout' period, after which time the two original intervention syringe exchange sites will become control sites and the two original control sites will become intervention sites. This cluster randomization scheme will help ensure that no neighborhood in San Diego County is denied access to the LinkUP intervention. By the end of the study, 75 LinkUP participants will have been randomized to an intervention site and 75 will have been randomized to a control site.

OnPoint peer counselors will confirm that their client is a LinkUP participant when they are presented with the laminated card that was provided by LinkUP staff. They will then conduct a short 5 minute interview with the participant to obtain information on their COVID testing and vaccination history, their health status and any of their harm reduction needs to facilitate any referrals. After their visit, the peer counsellor will supplement this

with the Out-take data, which includes whether or not the participant received the LinkUP intervention, COVID-19 test(s). The information obtained will be shared through record linkage between OnPoint and La Frontera to confirm the study outcomes including COVID-19 vaccination. Following the intake interview, the participant will either receive the LinkUP active or didactic intervention depending on the randomized allocation of the SSP site. LinkUP participants will be compensated \$10 for their visit at OnPoint regardless of whether or not they choose to undergo a COVID test or receive a COVID vaccine.

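### The analysis does not follow the four-site crossover: its only random effect is a subject intercept that the data cannot identify, and no firm provision is made for site, period or clustering

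*Combined protocol and SAP*

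**What the plan says.** Combined protocol and SAP, section 9, Cluster Randomization: "The four OnPoint syringe exchange locations will be randomized to deliver either the active (intervention) or didactic (control) version". The swap follows: "Approximately three months into enrollment, there will be a one-week" washout, after which, as section 11 repeats, "the two original intervention syringe exchange sites will become control sites and the two original control sites will become intervention sites". The target is that "75 LinkUP participants will have been randomized to an intervention site and 75 will have been randomized to a control site".

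Section 9, Analysis, is the only analysis text. It has three parts that matter here:

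- Per-arm results: "To obtain effect sizes and standard errors, percentages along with 95% CIs" are to be calculated for testing and for vaccination within six months. No interval method is named.
- A logistic mixed model, fitted separately for each outcome, is to supply the risk ratio. Arm is the main fixed effect, with "potential covariates (e.g., age, gender, homelessness, income) and a random intercept for subject".
- Baseline check: "We will compare socio-demographics across the two study arms (intervention and control) to ensure balance", then "controlling for potential confounders and study location if there are significant differences".

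No site or site-period effect, cluster-robust variance, ICC or small-sample correction is mentioned. No period term is named, although the covariate list is only illustrative.

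**The concern.** Arm is assigned by site and period, so the analysis should carry variation at that level. The one random effect in the model sits at the person level, where there is a single binary value per model and nothing to separate a person effect from the outcome itself.

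The follow-on decision rests on feasibility and acceptability, which this does not touch. But section 5 says the results will supply effect sizes for a later efficacy trial, section 7 places that trial at syringe programmes elsewhere in the country, and section 9 names standard errors as an output. If site variation is left out, the uptake rate in each arm will look better known than it is. For the comparison of arms, the reader cannot tell whether the stated precision is right.

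**Working it through.** **Inputs.** From section 9: 4 sites, 2 periods, 75 per arm. Hence 4 × 2 = 8 cells, 4 per arm, with m = 150/8 = 18.75 people per cell. The plan gives no power calculation, ICC, uptake rate or site volumes, so the only figure to reproduce is 150/2 = 75. Assumed here: 50% uptake; within-period ICC (ρ) of 0.02, 0.05 or 0.10; between/within-period ICC ratio (r) of 1, 0.8 or 0.5; equal cells unless stated.

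**1. Subject intercept.** Take illustrative results of 45/75 v 30/75 without covariates. For any fixed subject SD, the fixed effects can be chosen so that the marginal risks are 0.6 and 0.4. The maximised log-likelihood is therefore always 2 × (45 ln 0.6 + 30 ln 0.4) = −100.952.

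| Subject SD | Log-likelihood | Conditional OR | Marginal RR |
|---|---|---|---|
| 0 | −100.952 | 2.25 | 1.50 |
| 1 | −100.952 | 2.66 | 1.50 |
| 2 | −100.952 | 3.80 | 1.50 |
| 3 | −100.952 | 5.82 | 1.50 |

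The data cannot choose among these rows. The conditional odds ratio is arbitrary; the marginal risk ratio does not move.

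**2. Per-arm intervals.** Each arm contains each site once, so the crossover cancels nothing within an arm, whatever r is. Half-width = multiplier × √[0.25/75 × (1 + (m − 1)ρ)]. The multiplier is 1.96, or t on 3 df = 3.18 because an arm has only four cells.

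| ICC | 1 + 17.75ρ | Half-width, z (points) | Half-width, t on 3 df (points) |
|---|---|---|---|
| 0 | 1 | 11.3 | 18.4 |
| 0.02 | 1.355 | 13.2 | 21 |
| 0.05 | 1.888 | 15.5 | 25 |
| 0.10 | 2.775 | 18.9 | 31 |

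The z column shows the effect of clustering alone; the step to the t column is the price of having four cells. In simulation (12,000 runs per scenario) the ordinary per-arm 95% interval covered 94.8% with no clustering and 84.5–85.6% at ICC about 0.05.

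**3. Arm contrast.** Design effect = 1 + (m − 1)ρ − mρr. Ordinary standard errors are too small only if r is below (m − 1)/m = 17.75/18.75 = 0.947.

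| ICC | r = 1 | r = 0.8 | r = 0.5 |
|---|---|---|---|
| 0.02 | 1% too large | 3% too small | 7% too small |
| 0.05 | 3% too large | 6% too small | 16% too small |
| 0.10 | 5% too large | 11% too small | 26% too small |

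For example, at ICC 0.05 and r = 0.5: 1 + 0.8875 − 0.46875 = 1.419; 1 − 1/√1.419 = 16%.

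For 45/75 v 30/75, SE(log RR) = √(1/45 − 1/75 + 1/30 − 1/75) = 0.170, so RR = 1.50 (1.08–2.09). Scaling that SE by the root design effect gives 1.05–2.14 at ICC 0.05, r = 0.8, and 1.01–2.23 at ICC 0.05, r = 0.5.

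**4. Period.** Let s be the share of participants at the two sites that start as active, with each site's volume equal in both periods. The share of the active arm seen in period 2 is 1 − s, and of the control arm s. A 10-point change between periods therefore shifts the arm difference by 10 × (1 − 2s) points. With site shares of 45/25/20/10%, s reaches 0.70 and the shift is 4.0 points; with 30/27/23/20% it is at most 1.4; with equal sites, 0. Over the six possible allocations it averages zero, so this concerns the allocation actually drawn.

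**5. Site.** Stable site differences distort the contrast only if a site's volume changes between periods. The plan does not rule this out: people are sent to the nearest site, enrolment runs until 150 are reached, and the swap is by calendar time.

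**The case against.** Several stronger readings are tempting and should be resisted.

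- *The plan chooses to ignore clustering.* It does not say so. No interval method is named, the covariate list is open, and study location may enter. What stands is that nothing is specified and that location depends on a check whose named content is socio-demographic.
- *The arm comparison must be over-precise, as in a parallel cluster trial.* Not so. The crossover cancels stable site effects when cells are balanced, and at r near 1 ordinary standard errors are slightly conservative. The documents give nothing from which to fix r.
- *The subject intercept spoils the effect estimate.* The estimand is a risk ratio, and a marginal one is unchanged. Removing the term is housekeeping, although the plan does not say how the risk ratio will be obtained from the model.
- *Clustering turns ±11.3 into ±21 to ±31.* Much of that is the t multiplier, which alone gives ±18.4 at zero ICC.

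It can also be said that this is a pilot without efficacy power, and that intervals meant to describe only these four sites need not carry between-site variation. Both are fair. They limit the importance of the point, but they do not fit the stated use of the results to plan a trial elsewhere.

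**Conclusion.** The point holds as a specification gap that should be fixed; it does not undermine the pilot's aims. The mismatch between the site-level crossover and the person-level model is plain from the text and needs no assumed values.

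The sizes are conditional. If ordinary binomial intervals are used, the per-arm half-width should be larger by a factor of √1.355 = 1.16 to √2.775 = 1.67 at ICCs of 0.02 to 0.10, before any small-sample multiplier. For the arm contrast, both the size and the direction of the standard-error error are undetermined: nil or slightly conservative with r near 1, and 6–16% too small at ICC 0.05 with r of 0.8 to 0.5. A period trend matters only if site volumes are unequal. All ICCs, ratios, volumes and uptake rates are assumptions.

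**What to change.** 1. Delete the random intercept for subject.
2. Always include site and period as fixed effects, whatever the baseline comparison shows. Define period by the allocation in force when the participant is referred, because people attend when it suits them and may cross the swap.
3. Report the risk ratio as a marginal (standardised) estimate: predict every participant under active and under didactic from that model, then take the ratio of the mean risks.
4. Report events and denominators for the eight cells. Give per-arm percentages with intervals from the four cells (t on 3 df), and the risk difference from a cell-level regression on arm, site and period (8 − 1 − 3 − 1 − 1 = 2 df). Show ordinary intervals alongside, labelled as assuming no clustering.
5. If a site has no events, so that the logistic model has no finite fit, rely on the cell-level risk difference. This can happen: at an assumed 10% uptake without clustering, the chance that n people yield no event is 0.9ⁿ. The chance that at least one site is empty is then about 7.5% with 37.5 people per site and 28% with site totals of 68, 38, 30 and 14.
6. State that four sites give wide intervals and a poorly estimated ICC.

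A risk-ratio interval whose standard error is scaled by the between-cell Pearson statistic, with t on 2 df, is optional.

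**Cost.** Wording only; no new data or participants. With ordinary standard errors, adding site and period changes the median half-width of the risk difference from 15.9 points to 15.7 with equal cells and to 16.5 with cells of 34/19/15/7. That step alone does not cure clustering: at ICC about 0.05 and r = 0.5, simulated coverage was 88.8% for an unadjusted risk difference and 88.4% with site and period, against 95.3% for the 2-df analysis. The price is width. With no clustering, the 2-df half-width has a median of about 29 points (4.30 × 0.0816 × √ln 2, where 0.0816 = √(2 × 0.25/75)), against 1.96 × 0.0816 = 16 for an unadjusted ordinary-SE risk difference. A randomisation test is no way out: with six allocations its smallest two-sided p is 2/6 = 0.33.
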